As part of routine care, all adult CLL patients naïve to pneumococcal vaccination and cared for in the participating centers receive one dose of Prevenar13® followed by one dose of Pneumovax23® 2 months later. According to the current local standard of care for immunosuppressed individuals, the response to vaccination is assessed by measuring pneumococcal antibody levels before and 4-8 weeks after vaccination [16, 17]. In this non-interventional cohort study we will ask informed consent to all vaccinated CLL patients to collect their clinical data and laboratory results for study purposes.

4. Inclusion criteria

All adult CLL patients

- naïve to pneumococcal vaccination,
- having received one dose of Prevenar13®,
- followed by one dose of Pneumovax23® 2 months later,
- in whom pneumococcal antibody levels before and 4-8 weeks after vaccination are measured, and
- in whom a complete data collection is possible.

5. Data collection

After we obtain informed consent clinical data will be collected according to a standardized electronic case report form (Castor EDC). Variables included in the case report form are:

- sex
- smoking behaviour
- age at the moment of the PCV vaccine administration
- comorbidities (charlson comorbitiy index)
- before vaccination (as determined in the 6 weeks prior to vaccination)
 - Rai stage (I/II/III)
 - past or ongoing chemotherapy
 - ongoing steroid treatment
 - past or ongoing therapy with a monoclonal anti-CD20 antibody (and date of last infusion)
 - total IgG level
 - lymphocyte count, haemoglobin and platelet level
- pre-vaccination pneumococcal IgG levels
- post-vaccination pneumococcal IgG levels
- date of PCV and PPSV23 vaccine administration
- date of antibody measurements

Laboratory methods and definitions

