Serotype-specific pneumococcal immunoglobulin G (IgG) concentrations to 5 pneumococcal serotypes shared across both vaccines (6B, 9V, 14, 19F, 23F) and 4 serotypes unique to PPSV23 (8, 15B, 20, 33F) will be determined in the immunology laboratory of the UMC Utrecht. A validated multiplex immunoassay will be used (Luminex® technology). Serologic response will be defined as a \geq 4-fold increase in serotype specific anti-pneumococcal IgG for \geq 70% of measured. Serologic protection will be defined as an antibody concentration \geq 1.3 mcg/ml for \geq 70% of all measured serotypes, according to the definition of the *American Academy of Allergy, Asthma & Immunology* [18]. In addition, because most previous studies (Table 1) used the WHO cut-off for protection in infants (\geq 0.35 mcg/ml) we will also analyse our data by the infant correlate of protection to be able to compare our results with previous studies [19].

6. Data Analysis

The primary outcome of the study is serologic response rate (SRR) after vaccination. Secondary outcomes of interest are serologic protection rates (SPR) after vaccination analysed by the 2 most widely accepted serologic cut-offs described above, geometric mean antibody concentrations before and after vaccination, and factors associated with response to vaccination, such as age, treatment status and disease stage. To this end, we will perform a multivariable logistic regression analysis, starting with all previously mentioned clinical variables of interest and using a stepwise backward selection method based on p-value <0.1. For data analysis, we will use IBM SPSS version 24.0 (Chicago, Illinois) software. We will apply an α significance level of 0.05. Means and standard deviations will be presented for normally distributed data, and medians and interquartile ranges for non-normally distributed data. The χ 2 test will be used for dichotomous variables and the Student t test or Mann-Whitney U test for normally or non-normally distributed continuous variables, respectively. The Wilcoxon signed-rank test will be used to compare median pre- and post-vaccination antibody concentrations.

7. Ethical considerations and privacy

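### No adjusted analysis links the measured antibody concentrations to the clinical factors; the yes/no response flag alone can cost power, by an amount that depends on how a factor acts

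*Combined protocol and SAP*

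**What the plan says.** Section 6 (Data Analysis) makes the responder rate the primary outcome: "The primary outcome of the study is serologic response rate (SRR) after vaccination". The secondary outcomes include "factors associated with response to vaccination, such as age, treatment status and disease stage". The one model named for these factors follows: "we will perform a multivariable logistic regression analysis, starting with all previously mentioned clinical variables of interest", with backward selection at p < 0.1.

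The flag is defined under Laboratory methods and definitions in section 5. A patient responds with at least a "4-fold increase in serotype specific anti-pneumococcal IgG for" at least "70% of measured" serotypes. The assay covers "5 pneumococcal serotypes shared across both vaccines (6B, 9V, 14, 19F, 23F) and 4 serotypes unique to PPSV23".

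Concentrations before and after vaccination are both collected; the data list in section 5 includes "post-vaccination pneumococcal IgG levels". Section 6 states two uses for them: "geometric mean antibody concentrations before and after vaccination", and a Wilcoxon signed-rank comparison of pre with post. Neither involves a clinical factor. The t test, Mann-Whitney and chi-square tests are listed without saying what is compared. No sample size, power or expected response rate is given.

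**The concern.** Each patient contributes 9 × 2 = 18 concentrations, and the factor model appears to reduce them to one yes/no value. On that scale a 3.9-fold rise in all nine serotypes counts the same as no rise, and six responding serotypes count the same as none. Adding covariates does not recover this, because the loss is in the dependent variable.

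The factors are not incidental. Table 1 lists disease stage, total IgG and chemotherapy as associated with response in earlier CLL cohorts. A real effect of such a factor could drop out of the backward selection and be read as absent, although the study's own titres might show it.

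**Working it through.** The plan has no figure of its own to reproduce. The steps are the flag, the loss under a uniform shift, what that means for power, and the loss when a factor acts in another way.

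**1. The flag.** Serotypes measured: 5 + 4 = 9. Required: 0.7 × 9 = 6.3, so 7 of 9.

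**2. Loss under a uniform shift, single cut-off.** Assume normal log fold rises and a factor that shifts them by a small constant. With response rate p and z the (1 − p) normal quantile, the efficiency of the yes/no outcome relative to the continuous one is φ(z)² / [p(1 − p)].
- p = 0.10: z = 1.282, φ = 0.1755, 0.0308 / 0.09 = 0.342
- p = 0.20: z = 0.842, φ = 0.2800, 0.0784 / 0.16 = 0.490
- p = 0.50: z = 0, φ = 0.3989, 0.1592 / 0.25 = 0.637

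**3. The same for the 7-of-9 flag.** Assume nine log fold rises with unit variance and common correlation ρ, all shifted equally. The comparator is their mean, with variance ρ + (1 − ρ)/9. With P(μ) the probability of the flag at mean μ, the efficiency is [dP/dμ]² / [p(1 − p)] × [ρ + (1 − ρ)/9], found by numerical integration for ρ from 0.3 to 0.9. Loss is 1 minus efficiency.

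| Response rate | Loss, single cut-off | Loss, 7-of-9 flag |
|---|---|---|
| 10% | 66% | 66-70% |
| 20% | 51% | 51-57% |
| 24% | 47% | 47-53% |
| 30% | 42% | 43-49% |
| 50% | 36% | 37-44% |
| 58% | 37% | 38-45% |

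**4. Power, illustration only.** Assumed: binary factor split 50:50, effect 0.5 SD, two-sided alpha 0.05, single cut-off.

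| Analysis | Total N for 80% power | Power at an assumed N = 100 |
|---|---|---|
| Continuous | 126 | 71% |
| Flag, response rate 10% | 400 | 29% |
| Flag, response rate 24% | 246 | 43% |
| Flag, response rate 50% | 200 | 51% |

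**5. A factor that changes whether a patient responds.** Simulation with N = 100, 30% exposed and nine serotypes. Assumed responders: mean log2 rise 3.3, patient SD 0.6. Assumed non-responders: mean 0.4, SD 0.5. Residual SD 0.8. The flag is tested by chi-square and the mean log2 rise by t test, at alpha 0.05.

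| Probability of being a responder, by group | Overall flag rate | Power, flag | Power, mean log2 rise |
|---|---|---|---|
| 30% vs 5% | 20% | 82% | 78% |
| 50% vs 20% | 36% | 76% | 76% |
| 60% vs 30% | 45% | 72% | 74% |
| 15% vs 2% | 10% | 39% | 32% |

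A repeat of the first two rows gave 81% against 75% and 75% against 75%. Here the flag does as well as the titres, or slightly better.

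**6. Which response rate applies.** CLL response rates in Table 1 include 0%, 10-15%, 21%, 22%, 24%, 32% and 58.3%, and 100% in four patients without ibrutinib. The definitions differ. The 58.3% used a 2-fold rise in total anti-pneumococcal IgG, and the 100% needed a 2-fold rise in only 3 of 13 serotypes. Both rules are looser than a 4-fold rise in 7 of 9, so a low rate is plausible. Against that, the two cohort-wide 0% figures and the 22% come from PPSV23-only cohorts, and section 1 says that responses to the conjugate vaccines are higher and that the efficacy of the sequence is unknown.

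**The case against.** The strongest objection is that the loss belongs to the assumed data shape, not to the plan. Step 5 bears this out: when a factor separates responders from non-responders, the flag loses nothing material. That shape is not far-fetched, since Table 1 shows 0% with ibrutinib against 100% without, though with four patients in each group. This stands, and it makes the size of the loss conditional.

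Modelling the primary endpoint is also coherent. Who responds is a clinical question, and a mean-titre model answers a slightly different one. This stands too, and is why the titre model belongs beside the logistic model and should not replace it.

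That the flag is the only outcome of the factor analysis is an inference. The dependent variable is not named, and the unassigned t and Mann-Whitney tests could be used to compare titres between groups. Such comparisons would be unadjusted, so the absence of an adjusted titre analysis remains.

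A reader might infer that the plan always discards half or more of the information, or that the study will miss real factors. The documents support neither. Half or more needs both a roughly uniform shift and a response rate up to about 25-30%, and without a sample size, SD or effect size the chance of missing a factor cannot be computed. The power figures are also univariable at 5%, whereas the plan is multivariable with retention at p < 0.1.

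**Conclusion.** The concern holds in a conditional form. Section 6 names one factor model, a logistic regression whose natural outcome is the 7-of-9 flag, and plans no adjusted analysis of the concentrations against the clinical factors.

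Under a roughly uniform shift in log fold rise, the information lost is about 36-45% at response rates near 50-58%, about half at 20-25% and about two thirds at 10%. If a factor mainly changes whether a patient responds at all, the loss is small or nil. The documents do not say which pattern or which rate to expect. The figures further assume approximately normal log fold rises; values at the assay limits or serotype-specific effects would change them. Because the data are collected anyway, a prespecified titre model is a low-cost safeguard under either pattern.

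**What to change.** In section 6:

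1. Keep the serologic response rate as primary outcome and keep the logistic model. State that its dependent variable is the flag of at least a 4-fold rise in at least 7 of 9 serotypes.
2. Add one prespecified supporting model beside it: log2 post-vaccination IgG on log2 pre-vaccination IgG, serotype and the same clinical factors, with a random patient intercept. Report geometric mean ratios with 95% confidence intervals.
3. Tabulate the number of serotypes (0-9) per patient with at least a 4-fold rise.
4. State how values outside the assay range are handled, for example set to the limit, with a censored-model sensitivity analysis if they are frequent. SPSS MIXED fits a Gaussian model without censoring, so that analysis needs other software.
5. State that no factor will be reported as not associated with response on the flag model alone.

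The cost is a few lines of text, one extra model on data already collected and some work on out-of-range values. There are no added patient procedures. The downside is a second effect measure, a ratio of mean titres, whose question differs slightly from the odds of response.

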Pneumo-CLL study: Immunogenicity of the Currently Recommended Pneumococcal Vaccination Schedule in Patients with Chronic Lymphocytic Leukaemia.

PROTOCOL

Principal Investigator:	[name]
Co-investigator:	[name]
Writing committee:	[name]
	[name]
	[name]
	[name]
	[name]
	[name]
	[name]
	[name]
	[name]
	[name]
	[name]
	[name]
	[name]

1. Introduction

Patients with chronic lymphocytic leukaemia (CLL) are at increased risk of both invasive pneumococcal disease (IPD) and community acquired pneumonia (CAP) caused by Streptococcus pneumoniae [1-3]. Therefore, international guidelines recommend pneumococcal vaccination for all CLL patients, preferably before initiation of treatment. The recommended vaccination schedule consists of Prevenar13®, a 13-valent pneumococcal conjugated vaccine (PCV13) followed 2 months later by Pneumovax23, a 23-valent polysaccharide vaccine (PPSV23) [4, 5].

The immunological efficacy of this sequential vaccination schedule in CLL patients is unknown. Previous studies have only investigated responses to either PCV13 or PPSV23 alone (Table 1) [6-15]. Responses to PPSV23 alone are poor in CLL patients [7, 9, 10, 14, 15]. Responses to the 7valent pneumococcal conjugated vaccine (PCV7) or PCV13 are higher compared to responses to PPSV23, but lower compared to responses in healthy individuals [6, 8, 15]. More advanced disease stage and lower baseline IgG negatively influence responses to vaccination (Table 1) [6, 14, 15].

Study	Year	N (final	Population	Vaccination schedule	Serologic respone definition	Response rate	Factors associated with response	
analysis) A) Studies investigating schedules containing conjugated vaccines (PCV7/PCV13)								
Sinisalo et al (8)	2007	73	n=49 CLL (15% steroids, 22% chemo, 80% Binet A, median disease duration 2 years); n=24 healthy	PCV7 only	≥ 2 fold IgG rise AND serotype specific IgG ≥ 0.35 mcg/I for at least 6/7 PCV7 serotypes	24% CLL; 71% controls	Less advanced disease; no past or ongoing chemotherapy; normal IgG.	
Paiarski et al (6)	2014	39	Treatment naive CLL (n=24); Healthy (n=15)	PCV13 only	≥2 fold Total anti-pneumococcal IgG	58.3% CLL; 100% controls	Lower stage of CLL, higher total IgG	
Andrick et al (11)	2017	8	n=4 CLL + ibrutinib; n= 4 CLL - ibrutinib	PCV13 only	≥2-fold increase in 3 or more out of 13 serotypes	Ibrutinib 0%; No Ibrutinib 100%	Х	

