Svensson et al (15)	2018	128	Treatment naive CLL patients	PCV7 versus PPSV23 (RCT)	Serotype specific OPA titers to PCV13 serotypes > Lowel Limit of Quantification (OPA titers = interpolated reciprocal serum dilution resulting in complement- mediated killing of 50% of the assay bacteria)	PCV13: 32% ; PPSV23 21%	Less advanced disease; higher total I IgG	
Lindström et al (13)	2018	24	CLL, follow-up study of Sinisalo 2007	PCV75 years before	Serotype specific IgG≥0.35 mcg/I (per serotype)	For individual serotypes 29-71% of the patients were still protected	x	
Lindström et al (12)	2019	28	CLL (n=20); healthy controls (n=8), follow- up study of Sinisalo 2007		Serotype specific IgG for all PCV7 serotypes AND PPSV23 serotype 5 and 7	10-15%	Healthy controls had higher responses to all serotypes	
B) Studies	invest	igating PPS	SV23 only					
Hartkamp et al (14)	2001	24	57% Rai O-1; 28% prior chemothrapy; median disease duration >36 months	PPSV23	Protection: 2/3 serotypes 20% above cut-off based on reference adult hyperimmune plasma pool; Response: >2 fold increase + protection (definition above)	Response: 22% Protection: improved from 38% to 50% after vaccine;	Higher disease stage + lower baseline IgG; prior chemotherapy negatively impacted responses	
Sinisalo et al (7)	2001	27	n=14 Binet A, n=8 Binet B n=9 Binet C), median disease duration 3 years.	PPSV23	A significant proportionate change in total anti-pneumcoccal IgG (no cut off value given)	0% :-	x	
van der Velden et al (9)	2007	49	CLL >50% RAI 0; 20% previous chemotherapy	PPSV23 (with or without ranitidine)	Response =>4 fold increase in IgG to 3 serotypes; Protection: ≥0,35 mcg/ml	response; 'Protection' increased from 45%-59%	Ranitidine did not generate better responses	
Safdar et al (10)	2008	32	87% had previous chemotehrapy and 73% anti-CD20	PPSV23 (n=7); PPSV23 + G-CSF injections (n=25)	≥2-fold IgG rise and level >0.5mcg/ml for all 6 measured seorypes	0% (0-17% per individual serotype)	G-CSF did not generate better responses	

2. Objective

The aim of this observational cohort study is to assess the immunogenicity of the currently recommended vaccination schedule of PCV13 followed by PPSV23 in CLL patients.

3. Study design

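### Backward selection at p<0.1 from an unlisted starting set, with only the survivors reported, overstates moderate associations with vaccine response if the cohort is about 100–150

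*Combined protocol and SAP*

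**What the plan says.** Section 6 (Data Analysis) lists among the secondary outcomes "factors associated with response to vaccination, such as age, treatment status and disease stage". The method is multivariable logistic regression, "starting with all previously mentioned clinical variables of interest and using a stepwise backward selection method based on p-value <0.1". The same section adds "We will apply an α significance level of 0.05" and "For data analysis, we will use IBM SPSS version 24.0".

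The starting set is not listed. On a broad reading it is the case report form in section 5, which gives twelve candidates: sex, smoking, age, Charlson index, Rai stage, chemotherapy, steroids, anti-CD20 therapy, total IgG, and the three items in "lymphocyte count, haemoglobin and platelet level". On a narrow reading it is the three examples in section 6. The form also holds "pre-vaccination pneumococcal IgG levels", which could be a thirteenth candidate; the plan does not say.

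The plan provides no full-model reporting, shrinkage, resampling or exploratory label for this analysis. It gives no sample size, expected response rate or number of responders per candidate. It does not mention confidence intervals for odds ratios.

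**The concern.** A term appears in the final model only if its p-value is below 0.1. Its estimate and p-value are then read at the 0.05 level as if the model had been fixed in advance. Two consequences follow for what is reported. A moderate effect estimated by chance near its true size may be dropped, while the same effect estimated too high is kept. A factor with no effect that gets through has already passed half of the test it is then judged by.

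Readers will take the retained factors as evidence about which CLL patients respond to the schedule. Because the candidates are unnamed and removal is data-driven, the final model is also undefined until the data are seen.

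**Working it through.** **Inputs.** From section 6: retention at p<0.1 and a level of 0.05 (taken as two-sided). From section 5: 12 candidates on the broad reading. From section 6: 3 on the narrow one. The plan has no figure to reproduce.

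**Assumed.** N = 100 and 150; response rate (SRR) 15%, 24% and 50%. The 24% is in Table 1 ("24% CLL; 71% controls"), under another schedule and definition. The 15% and 50% are scenarios; the table also shows 58.3%, above the range used.

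**1. Retained null factor.** P(p<0.05 given p<0.10) = 0.05/0.10 = 50%. This does not depend on N. In simulation the 95% CI of a retained null included 1 in 47–51% of cases (12 candidates) or 46–56% (3). With pairwise correlation 0.2 it was 41–48%.

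**2. Unconditional false positives.** In a simulation with 12 independent candidates (N = 100, 150, 300; SRR 24%, 50%), a null factor reached p<0.05 in 5.0–6.1% of runs after selection and 5.1–6.2% in the full unselected model. With correlation 0.3 the figures were 6–7% against 5–6%.

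**3. Moderate effect, true OR 1.5 per SD.** Simulation with 2000 runs per cell, independent candidates, one true factor and Wald removal. Entries are median ORs.

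| N / SRR | 12 candidates: survivors (retained) | 12 terms, unselected | Difference | 3 candidates: survivors | 3 terms, unselected | 5-term Firth, all runs |
|---|---|---|---|---|---|---|
| 100 / 15% | 2.07 (43%) | 1.68 | 0.39 | 1.98 | 1.54 | 1.49 |
| 100 / 24% | 1.85 (53%) | 1.62 | 0.23 | 1.79 | 1.53 | 1.49 |
| 100 / 50% | 1.76 (61%) | 1.59 | 0.17 | 1.71 | 1.53 | 1.49 |
| 150 / 15% | 1.82 (57%) | 1.60 | 0.22 | 1.77 | 1.54 | 1.51 |
| 150 / 24% | 1.70 (67%) | 1.58 | 0.12 | 1.67 | 1.53 | 1.51 |
| 150 / 50% | 1.61 (75%) | 1.54 | 0.07 | 1.58 | 1.50 | 1.48 |

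The full 12-term fit failed in 5–6% of runs at 100 / 15%, so that row is the least secure.

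**4. Check by normal theory.** With Z ~ N(μ, 1) and c = 1.645, the mean of Z given retention is μ + [φ(c−μ) − φ(c+μ)]/P(retained). At 50% retention μ is about 1.645, which gives 1.645 + (0.399 − 0.002)/0.50 = 2.439. The coefficient is inflated by 2.439/1.645 = 1.48, so OR 1.5 becomes exp(1.48 × 0.405) = 1.82, in line with 1.85 in the table at 53% retention. At 88% retention, μ = 2.82 and the ratio is (2.82 + 0.200/0.88)/2.82 = 1.08, or OR 1.55.

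**5. Larger N.** At N = 300 survivors had medians of 1.54–1.57 against 1.52–1.54 unselected. A further simulation (three true factors, correlation 0.2) gave survivor medians of 1.61–1.67 at N = 200 and 1.53–1.54 at N = 400.

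**6. Stronger effect, true OR 2.0, N = 100–150.** Survivors 2.10–2.38; unselected 12-term model 2.16–2.35; five-term Firth model 1.94–2.00. Here the excess comes from too many unpenalised terms, not from selection.

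**The case against.** **False positives.** A reader might infer from the one-half figure that selection produces many extra false findings. Step 2 does not support this. The figure holds for any 5% test looked at only when p<0.1. The chance of at least one false positive across the null factors was 42–47% after selection and 42–48% without it. The invalid intervals are also an inference, since the plan promises none; but the same conditioning applies to the final-model p-values.

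**Overstatement as a general fact.** The plan states no N, and it invites all vaccinated CLL patients in the participating centres, so a large cohort is not excluded. If dropped terms are counted as zero, the average coefficient for OR 1.5 was 0.90–1.02 of the truth in the simulation with three true factors. At OR 2.0 survivors were closer to the truth than the unselected model in five of six cells. All of this stands: the distortion lies in what is reported, and its size is conditional on N and on the effect.

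**Little gain from penalisation.** If a reader looks at the five-term Firth model only when p<0.1, the median is 1.57–1.93, close to the 1.61–2.07 for survivors. This also stands. Most of the gain comes from reporting every term.

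**Baseline antibody.** Pre-vaccination IgG is the denominator of the fold-rise outcome, and a reader might infer that the planned model is biased without it. The documents do not support that. They neither exclude it nor force it in, and adjusting for it is a choice about the question, since it may lie on the path from stage or total IgG to response. Any figure for its effect would need slopes and correlations that the documents do not give.

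**The narrow reading.** Starting from three candidates does not remove the problem: survivors are at 1.58–1.98 against 1.50–1.54 unselected.

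**Conclusion.** The point holds in conditional form, as a cheap improvement to one secondary analysis. At N of about 100–150, selection moves the reported median for a true OR of 1.5 up by 0.07–0.39 beyond the unselected 12-term model, which is itself somewhat high at 1.54–1.68. The size rests on the assumed N, response rates and effect. The one-half result for retained nulls needs no such assumption, but it describes the retained factors only and is not an error rate of the analysis as a whole. The unlisted starting set is a plain gap in the text whatever the cohort size.

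**What to change.** Replace the selection sentence in section 6 with text such as:

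> One prespecified logistic model for serologic response will be fitted once, without variable selection. It will contain age, Rai stage (one ordinal term), treatment status (chemotherapy, anti-CD20 and steroids, combined or as separate terms, fixed before analysis) and total IgG. Firth-penalised odds ratios with 95% confidence intervals will be reported for every term whatever its p-value. Other case report form variables will be reported univariably, as description only. A model that adds mean log10 pre-vaccination pneumococcal IgG will be a sensitivity analysis. The factor analysis is exploratory.

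Section 1 and Table 1 already point to stage, IgG and treatment (for example "prior chemotherapy negatively impacted responses"), and all these variables are collected. The investigators may choose another short list, provided that it is named before analysis. If all twelve must be adjusted for, a 12-term Firth model reported in full is also defensible: at N = 100 its mean coefficient was 1.01–1.02 of the truth.

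Costs:
- Fewer variables get an adjusted estimate; a true factor outside the model gets only a univariable one.
- Intervals will be wide. At N = 100–150 and SRR 15–24%, responders per term run from 100 × 0.15/7 = 2.1 (seven terms, with the sensitivity term) to 150 × 0.24/4 = 9.0 (four terms). This is the reason to prefer penalisation.
- If all terms are null and independent, the chance of any p<0.05 is 1 − 0.95^4 = 19% for four terms and 1 − 0.95^7 = 30% for seven. Testing the six remaining variables as well as a four- or six-term model would give 1 − 0.95^10 = 40% or 1 − 0.95^12 = 46%, so they should stay descriptive.
- The simulated Firth models had five, seven or twelve independent or mildly correlated terms; total IgG and pneumococcal IgG together may be more strongly correlated.
- The Firth fit may need software beyond the SPSS version named.
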